## 15.7 Subgroup Analyses

### 15.7.1 Interaction Between CAD Presentation and Genotype-guided Therapy

We will analyze the primary endpoint of MACE between reduced function allele carriers on clopidogrel versus those on ticagrelor within ACS presentation class, stable CAD, unstable angina/NSTEMI, and STEMI. We will test for the significance of the interaction between CAD presentation and genotype-guided antiplatelet therapy with a Cox proportional hazards model.

### 15.7.2 Interaction Between \*17 Carriers and \*2/\*3 and Antiplatelet Therapy

We will analyze MACE and bleeding endpoints with Cox proportional hazards models with main effects for \*17 allele carrier, \*2/\*3 carrier and clopidogrel vs. ticagrelor therapy. We will test for interactions between antiplatelet therapy and \*17 allele, plus interaction between \*17 and \*2/\*3 alleles.

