Overall, preliminary studies have demonstrated an association between *CYP2C19* reduced function alleles, clopidogrel response, and outcomes in patients undergoing PCI. These studies have all been retrospective in nature and a recent large meta-analysis suggests no significant association between *CYP2C19* genotype and cardiovascular events with clopidogrel use. Whether such patients with 1 or 2 *CYP2C19* reduced function alleles might benefit from alternative anti-platelet therapy is controversial and has not yet been studied in a prospective, randomized fashion.

The RAPID GENE study randomized 187 patients undergoing PCI for ACS or stable coronary disease to a strategy of rapid point-of-care genotyping or to standard treatment. For patients assigned to the rapid genotyping strategy, those that were identified as carriers of the *CYP2C19*\*2 allele were switched to prasugrel, while non-carriers and those in the standard treatment group received clopidogrel 75mg daily. The strategy of rapid genotyping in conjunction with personalized antiplatelet therapy, led to a reduction in HPR in *CYP2C19*\*2 carriers compared to those in the standard group (0% vs. 30.4%). In the study, the point-of-care genetic test demonstrated a sensitivity of 100% and a specificity of 99.3%. These results provided the proof-of-concept that bedside genotyping was feasible and accurate.

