In Caucasians, the \*2 allele frequency is 15-20% and \*3 allele frequency is less than 1%, but up to 29% and 9%, respectively, in Asians. Although we are genotyping for \*3, because of its low frequency in our predominant Caucasian population, we expect to detect very few such patients in Rochester (more may be expected from the Canadian, Arizona, and Florida sites). We expect (assuming Hardy-Weinberg equilibrium) approximately 4% of patients to be homozygous for the \*2 allele (\*2/\*2), 32% to be heterozygous for the \*2 allele, and 64% to be WT. Thus, we will expect around 36% of patients that go on to PCI will be carriers of one or two \*2 alleles. However, to be conservative we will estimate 30% of the 4,255 enrolled Caucasian patients and 50% of the 1,015 Asian patients, or ~ 1,784 patients to be carriers of the *CYP2C19* reduced function allele. After randomization, we anticipate there will be approximately 892 patients in each group, i.e. the conventional therapy group receiving clopidogrel who are retrospectively identified to have *CYP2C19* reduced function allele and the prospectively genotyped group whose therapy was guided by the Spartan device results and are retrospectively identified to have *CYP2C19* reduced function.

The *CYP2C19*\*17 allele frequency in Caucasians is approximately 21-23% and 3% in Asians, and it occurs at a frequency of ~26% of Caucasian patients with the \*2 allele. The \*17 allele is considered a gain-of-function allele and has been shown in some studies to lead to enhanced response to clopidogrel (via platelet function testing) and a higher rate of bleeding events. However, other studies have not demonstrated increased platelet inhibition or altered clinical outcomes with the \*17 allele. Taken together, it is unclear how patients with the \*17 allele would respond to clopidogrel, and the combined effect of \*2 and \*17 on *CYP2C19* function and response to clopidogrel is additionally uncertain. Therefore, for the purposes of this study, \*17 will not be taken into consideration for prospective treatment decisions. However, we will utilize the \*17 information to perform retrospective secondary analyses to determine its effect (alone and in the presence of \*2 or \*3) on bleeding risk and MACE.

[figure not shown]

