that point forward will be from Korea. This is lower than observed so far (30%), due to the impending activation of additional sites in North America. Increasing this percentage would result in a smaller required sample size, as it would increase the prevalence of LOF subjects in the study. We also assume that the current prevalence of LOF carriers will continue in Korean (59%) and North American (28%) subjects. Increasing either of these prevalences would reduce the number of subjects required. The power calculations are based on a two-sided log-rank test at a Type I error rate of 0.05 with an expected randomization ratio of 1:1. Table 3 demonstrates the calculations for total subjects enrolled assuming an event rate of 4.5%. Table 4 gives required sample sizes for varying event rates and power levels. These tables show that the previous planned sample size of 5270 subjects provides at least 80% power if the event rate is at least 4.0%.

**Table 4.** Revised Sample Sizes for a Minimum Detectable Hazard Ratio of 0.50 with an overall event rate of 4.5%

	80% Power	85% Power	90% Power
N of LOF subjects required	1560	1784	2086
N of LOF subjects accounting for 5% dropout	1643	1878	2196
N of LOF patients expected from Korea	747	828	937
N of LOF patients expected from North America	896	1050	1259
Total patients expected from Korea	1275	1413	1599
Total patients expected from North America	3192	3742	4486
Total number of patients to enroll	4467	5155	6085

**Table 5.** Required Sample Sizes for a Minimum Detectable Hazard Ratio of 0.50 at varying event rates and power assumptions

Baseline event rate	Power at n=5270	Sample size needed for given power		
		80%	85%	90%
5.0%	89.3%	3955	4570	5409
4.5%	85.8%	4467	5155	6085
4.0%	81.6%	5052	5827	6875

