
### 15.9.2 Event Rate in Subjects Enrolled at Korean Sites

Similarly, there is some concern that the event rate for the primary endpoint may be substantially lower in patients enrolled at Korean sites. We will follow a similar procedure as above to safeguard the power of the trial. Once the first batch of TaqMan results is available for the conventional arm subjects, we will monitor event rates monthly within the reduced function subjects of this arm and quit enrollment of subjects at Korean sites if the event rate for primary endpoint is *significantly lower* than that of subjects enrolled at non-Korean sites and we are *nearly certain* that continued enrollment in Korea will reduce the study power below 75%. *Significance* of the difference between Korean-enrolled and non-Korean enrolled subjects in the conventional treatment arm will be assessed by a one-sided log rank test conducted at a 0.005 Type I error rate. The assessment of study power will be conducted using Bayesian estimation methods. The 1- year event rate will be estimated from the reduced function subjects in the conventional treatment arm. Using Bayes Theorem we will calculate the posterior distribution of study power, given the current event rate and a prior distribution for the event rate (beta distribution with a mean of 0.12 and 99% of the probability density between 0.04 and 0.20), while maintaining the initial study design assumptions of hazard ratio and sample size. In particular, we will calculate the probability that the power of the study will exceed 75%. We will be *nearly certain* that continued

enrollment will reduce the study power below 75% if the aforementioned probability is less than 1%.

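### The \*17 model in Section 15.7.2 names no region, site or CAD-presentation term, so as written its non-randomised genotype effects would absorb any Korean versus North American difference in event rate (minor; exploratory analysis).

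*Combined protocol and SAP*

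**What the plan says.** Section 15.7.2 gives the \*17 analysis: "We will analyze MACE and bleeding endpoints with Cox proportional hazards models with main effects for" \*17 carrier, \*2/\*3 "carrier and clopidogrel vs. ticagrelor therapy". It then adds tests of \*17 by therapy and \*17 by \*2/\*3. No covariate, stratum or allele count is mentioned.

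Other sections show how genotype and region are linked:

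- Section 5, on \*17: "allele frequency in Caucasians is approximately 21-23% and 3% in Asians".
- Section 15.2.2, on LOF carriage: "prevalence of LOF carriers will continue in Korean (59%) and North American (28%) subjects".
- Section 15.9.2: "there is some concern that the event rate for the primary endpoint may be substantially lower in patients enrolled at Korean sites".
- Sections 5 and 6.1: U.S. sites enrol both ACS and stable CAD, and international sites enrol ACS only. Section 15.9.1 allows that stable CAD may have a substantially lower event rate.

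Elsewhere the plan does mention adjustment. Section 15.5 puts the randomisation variables (age, sex, site, CAD presentation) and other predictors of MACE into the primary model. Section 15.6 promises suitable but unlisted covariates for secondary analyses of one-year endpoints. Section 2.3 lists the \*17 question as exploratory, and Section 15.7.3 calls the subgroup analyses exploratory.

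**The concern.** Randomisation protects the comparison of drugs within LOF carriers. It does not protect \*17 versus no \*17, or LOF versus wild type. Those contrasts compare groups with very different proportions of Korean patients. Korean patients also differ in presentation by design, because international sites take ACS only.

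If the baseline hazard differs by region for any reason, a model without region or site attributes part of that difference to genotype. A \*17 or LOF association with MACE could then appear, shrink or change direction because of the enrolment mix alone. At stake are exploratory outcome 2 in Section 2.3 (\*17 on MACE and bleeding) and, if they were fitted in the same way, the genotype comparisons in items 4 and 5.

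**Working it through.** **Plan's own figure first.** Table 4 expects 1,413 Koreans at a total of 5,155, and Section 15.2.2 assumes 20% Korean enrolment from there. At 5,270 this gives 1,413 + 0.20 × 115 = 1,436 Korean and 3,834 North American patients.

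- LOF carriers: 0.59 × 1,436 + 0.28 × 3,834 = 1,921.
- After 5% dropout, 1,825; at 4.5%, 82 events.
- Freedman's formula at HR 0.50: z = √82.1 × (0.5/1.5) − 1.96 = 1.06, so power is 85.6%. Table 5 states 85.8%, so these regional inputs are the plan's.

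**Allele frequencies** (Hardy-Weinberg within region, with Korean = Asian and North American = Caucasian).

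- LOF: 1 − √(1 − 0.28) = 0.151 in North America and 1 − √(1 − 0.59) = 0.360 in Korea. Section 5 gives \*2 and \*3 as "up to 29% and 9%, respectively, in Asians", an upper limit of 38%, which is consistent.
- \*17: 0.22 and 0.03. Carriage is 1 − 0.78² = 39% and 1 − 0.97² = 5.9%.
- Check: with \*17 and LOF as alternative alleles, 2 × 0.151 × 0.22 × 3,834 ≈ 256 of 1,074 North American LOF carriers have \*17, or 24%. Section 5 says that \*17 "occurs at a frequency of ~26% of Caucasian patients with the" \*2 allele.

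**Expected cells at 5,270**

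| Cell | North America | Korea |
|---|---|---|
| Wild type, no \*17 | 1,514.6 | 534.9 |
| Wild type, \*17 | 1,245.9 | 53.9 |
| LOF, no \*17 | 818.0 | 816.2 |
| LOF, \*17 | 255.5 | 31.0 |

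Korean share: 85/1,586 = 5% of \*17 carriers against 1,351/3,684 = 37% of non-carriers; 847/1,921 = 44% of LOF against 589/3,349 = 18% of wild type.

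**Spurious effects with no true genetic effect.** Let r be the Korean:North American rate ratio. The documents give none, so it is assumed. The average relative rate in a cell is (N_NA + r × N_K)/(N_NA + N_K). At r = 0.5:

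- \*17 HR (within wild type): [(1,245.9 + 27.0)/1,299.8] ÷ [(1,514.6 + 267.5)/2,049.5] = 0.979/0.870 = 1.13.
- LOF HR (without \*17): [(818.0 + 408.1)/1,634.2] ÷ 0.870 = 0.750/0.870 = 0.86.
- \*17 × LOF: (0.946/0.750)/1.126 = 1.12.

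A Poisson fit of the full 15.7.2 structure to expected counts, at a 4.5% North American rate, gives the same values:

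| r | \*17 HR | LOF HR | SE of \*17 log HR |
|---|---|---|---|
| 0.5 | 1.13 | 0.86 | 0.17 |
| 0.7 | 1.07 | 0.92 | 0.17 |
| 1.0 | 1.00 | 1.00 | 0.17 |
| 1.3 | 0.94 | 1.07 | 0.16 |

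A true ticagrelor HR of 0.65 is returned as 0.65 at every r. Adding a region term returns every genotype HR to 1.00. At r = 0.5 the SE of the \*17 log HR moves only from 0.173 to 0.175.

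**Allele count.** A patient with two LOF alleles cannot carry \*17. These patients number 0.151² × 3,834 + 0.360² × 1,436 ≈ 88 + 186 = 274, or 14% of LOF carriers, and all fall in the LOF cell without \*17 (274/1,634 = 17% of it). With the HRs of 1.55 (one allele) and 1.76 (two) that Section 4 cites from a nine-study meta-analysis, equal regional rates and no gradient on ticagrelor, yes/no coding gives \*17 × LOF 0.98 and \*17 × therapy 1.02. The bias is about 2%, against log-scale SEs of roughly 0.4 to 0.5.

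**The case against.** The strongest reply is that 15.7.2 names the terms of interest and does not exclude others. Section 5 calls the \*17 work secondary, Section 15.6 promises covariates for secondary MACE and bleeding analyses, and the primary model includes site, which determines region. A reader might infer that the plan has decided to leave region out. The documents do not show that; they show that no region term is specified. The reply does not remove the point, however. Section 15.6 concerns comparisons by randomised arm, Section 2.3 lists \*17 as exploratory, and Section 15.6 names no variable. Region adjustment is not pre-specified on either reading.

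Four other stronger readings also go too far:

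- **That genotype effects will be biased in a known direction.** Section 15.2.1 planned on 12% in Koreans as well, which means a ratio of 1.0 and no bias. Section 15.9.2 voices a concern and gives no figure. ACS-only enrolment abroad could push the Korean rate up relative to sites that also take stable CAD.
- **That the LOF versus wild-type comparison (2.3, item 4) will come from this model.** No section assigns it a model.
- **That yes/no LOF coding confounds the LOF effect.** For the main effect it averages one- and two-allele carriers, which is pooling. Only the interactions can be distorted, by about 2% under the cited HRs.
- **That the trial cannot speak to one-allele carriers.** They are about 86% of the LOF group, so its result is mainly theirs.

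It also stands that the bias is small against noise. At r = 0.5 the \*17 log HR is off by 0.12 against an SE of 0.17.

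**Conclusion.** The point holds as a minor one. Fitted with only the listed terms, the 15.7.2 model confounds the \*17 and LOF effects with region whenever regional event rates differ. Over assumed ratios of 0.5 to 1.3, the spurious \*17 HR runs from 1.13 to 0.94 and the spurious LOF HR from 0.86 to 1.07. There is no bias at a ratio of 1.0, and its sign cannot be known in advance.

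These figures rest on Hardy-Weinberg proportions within region, on equating region with ancestry, on \*17 at 22% and 3%, and on a 4.5% North American rate. Only MACE was worked through, because the documents give no regional bleeding rate. Hypothesis 1A and the randomised drug contrast are not affected.

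**What to change.** In Section 15.7.2, state that the Cox models are stratified by region (Korea versus non-Korea) or by site, and adjusted for CAD presentation and the other randomisation factors. State the same adjustment for the non-randomised genotype comparisons in Section 2.3, items 4 and 5, and say which model those comparisons use.

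As an optional sensitivity analysis only, repeat the \*17 interaction model with LOF allele count (0/1/2) in place of carrier yes/no.

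The cost is SAP wording. Site, age, sex and CAD presentation are randomisation factors, and the TaqMan genotype is already planned for every patient. The loss of precision from a region term is negligible (SE of the \*17 log HR 0.173 to 0.175 at r = 0.5).

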## 15.8 Monitoring for Futility and Efficacy

Both efficacy and futility monitoring require three estimates: 1) a best current estimate of the treatment effect, as well as 2) uncertainty of the estimate (standard error and/or confidence interval), and 3) an estimate of what proportion of the study's final information is currently in hand, that is, the current value of "information time".

Information time is critical both in assessing conditional power (futility) as well as in doing interim testing using group sequential approaches. Appendix C details how to

construct a combined likelihood combining the information from the complete and the incomplete subject data, which produces the first two required estimates, using likelihood calculations, and specifically, using the profile likelihood method to get down to the one-dimensional likelihood for the treatment effect parameter.

Appendix C also details how to estimate information time (the third required measure). Once we have a current z-score (effect divided by standard error) for the treatment effect, as well as our current estimate of information time, we can then do standard calculations for conditional power (futility) and efficacy

**Futility Monitoring:** We propose that this assessment be based on our calculation of conditional power, as described in Appendix C. In addition to the conditional power calculation, we will provide the modified unconditional power calculation based on current estimates of event rates and the estimate and 95% CI of the average event rate in LOF subjects. We specifically propose that at the time of DSMB reviews, that consideration be given to stopping the trial if the ratio of conditional power to initial power falls below the proportion of remaining information time. For example, if the initial power is 85%, and the proportion of remaining information time is 40%, then the conditional power should exceed 34% ( $0.85 \times 0.4$ ). The basis for the moving target of conditional power is the “sunk cost” argument. The initial study design is assumed to equate the expected utility of a positive result with the cost of the entire study. By equating the ratio between conditional power and initial power, the cost-benefit ratio is maintained. This means that the bar for conditional power for continuing gets progressively lower, as more of the total study costs become a “sunk cost.”

**Efficacy Monitoring:** Although we neither recommend, nor anticipate, stopping early for efficacy, we recognize the need to provide for an exit strategy that permits a statistically valid conclusion to be drawn when it is desired to stop the trial and claim efficacy. We therefore propose using the efficacy stopping boundary proposed by Peto and Haybittle, namely we use a 2-sided nominal p-value of 0.001 for all interim looks (critical value 3.291), where the looks are at 40%, 60%, and 80% of information time, and we are thereby entitled to conduct the final test at the 0.0495 level (critical value = 1.965 rather than 1.960). This procedure accommodates the fact that our knowledge of information time is limited by the vagaries of incomplete (and changing) endpoint ascertainment and incomplete genetic ascertainment. The use of a fixed critical value independent of information time is very helpful in this unique context of uncertainty around the precise value of information time. This means a critical value of 3.291 would obtain at any interim look, independent of at what interim time the look occurred. At the final look, the critical value of 1.965 rather than 1.96 will be applied, which has an infinitesimal impact on power. We propose up to 3 interim looks, and that these occur at information times of approximately 40%, 60%, and 80%.

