### 15.2.2 Revised Sample Size Calculations

At the time of this protocol revision (Version 8), the estimated event rate for the primary endpoint across all LOF subjects is 4.8%, substantially lower than the assumptions made in Section 15.2.1. We propose performing updated power calculations using a revised minimum detectable effect of a hazard ratio of 0.50. This effect size is justified by several arguments. First, ticagrelor has already been shown to reduce MACE events by about 16% in all ACS patients, regardless of genotype, in the PLATO trial. However, because our study treatment represents a precision medicine, pharmacogenomic approach, we expect a much greater treatment effect in the targeted LOF population. Second, such effect sizes have been seen in other studies involving CYP2C19 \*2 and \*3 alleles(2,40). Third, a meta-regression analysis of studies comparing event rates in (primarily) clopidogrel-treated patients who were LOF vs. WT suggested an inverse relationship between the overall event rate and the WT vs. LOF advantage, such that the predicted HR

in very low event rates was consistent with 0.50. Finally, at low event rates, a large effect must exist within the LOF population in order to achieve reasonable number-needed-to- treat (NNT) values, since the genotype-guided dual antiplatelet treatment is expected to have no effect in the WT population. For example, if the event rate is 4% in LOF subjects on clopidogrel, and 2% in LOF subjects on ticagrelor, that 50% reduction would equate to a NNT of 50 subjects within the LOF sub-population. If the prevalence of LOF alleles is 30% in the overall population, that would equate to an NNT of 167. Under initial assumptions, the NNT in the LOF sub-population would have been 25 subjects, equating to an overall NNT of 75. Thus, from the perspective of NNT, we are powered to detect a smaller effect than under initial assumptions.

Additional assumptions play a role in the power calculations. First, we assume that around the total enrollment mark of 3900 subjects, 20% of subjects enrolled from

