where  $L_1$  and  $L_3$  have the obvious definitions parallel to the 'known-genotype' likelihoods spelled out above. If this were the only data available, then the 4 parameters ( $\lambda_1, \lambda_2, \lambda_3, \alpha$ ) would not be identifiable, i.e.  $\alpha$  and  $\lambda_3$  would be completely confounded. However, we have one further piece of data: the numbers of LOF and WT subjects in the PG group. These numbers can be put into a binomial likelihood with  $\alpha$  as the only parameter. The random variable corresponding to this proportion is statistically independent (at least uncorrelated), with all the other likelihood pieces. Therefore, the overall likelihood is the product of all the conditional likelihood pieces for the members of the 3 groups, along with this binomial likelihood for the prevalence of LOF. This serves to identify both  $\alpha$  and therefore  $\lambda_3$  as parameters. Thus in this complete likelihood, all 4 parameters are identified. Thus, the *incomplete* data provides a likelihood that *is* informative about the treatment effect (subject to the null hypothesis assumption regarding the effect of knowledge of genotype on the WT/CLOP response). The likelihood from these data can be combined with the simple TaqMan binomial data to derive a combined likelihood which incorporates both pieces of information.

*Estimation of Information Time:* We can also estimate the proportion of total study information contained in the current data. First, we estimate the expected information at the end of the trial as the

inverse of the expected square of the standard error of the hazard ratio of interest. Our expected power of 85.8% implies that our expected z-score at the end of the trial is 3.031. Given a minimum detectable effect size of 0.50, the expected standard error at study end is 0.2287 ( $\log(0.5)/3.031$ ). Thus the expected final information is 19.1. Second, the available information in the current data is calculated using a profile likelihood approach to estimate the standard error of the current estimate of the treatment effect. The ratio of the current information to the expected final information is the estimated information time.

*Calculation of conditional power:* Conditional power is a function of the current effect estimate z-score and information time. Its formula is:

$$CP(t, Z_t) = 1 - \Phi\left[\frac{\Phi^{-1}(0.975) - Z_t \sqrt{t}}{\sqrt{(1-t)}}\right] - (\Phi^{-1}(0.975) + \Phi^{-1}(P_0)) * \sqrt{(1-t)}$$

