### G. Data and Safety Monitoring Board

A data and safety monitoring board (DSMB) will be assembled twice per year to ensure data quality and participant safety and to provide independent advice to the Steering Committee regarding progress and the appropriateness of study continuation. Minutes will be taken during each meeting and shared with each site. The Mayo statistician will generate statistical reports for the DSMB. If the assumptions upon which the power and sample size calculations were based appear not to hold in the enrolled patients (e.g. the primary endpoint rate is lower than expected), the DSMB may advise the Steering Committee to modify the protocol to allow a larger sample size. At least one additional member will be added to the DSMB to review the digital follow-up sub-study with relevant technology experience.

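### The powers in Table 5 and the claim of at least 80% at a 4.0% event rate leave out the section 15.8 futility guideline; if it is followed, power is about 83% at 4.5% and 78% to 80% at 4.0%

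*Combined protocol and SAP*

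**What the plan says.** Section 15.2.2 bases the revised calculation on a "two-sided log-rank test at a Type I error rate of 0.05 with an expected randomization ratio of 1:1" and a "revised minimum detectable effect of a hazard ratio of 0.50". Table 4 takes a 4.5% event rate as the base case. Table 5 lists power at 5270 subjects as 89.3%, 85.8% and 81.6% for event rates of 5.0%, 4.5% and 4.0%. The text concludes that the "previous planned sample size of 5270 subjects provides at least 80% power if the event rate is at least 4.0" percent.

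Section 15.8 adds two kinds of monitoring.

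- **Futility.** At DSMB reviews it proposes that "consideration be given to stopping the trial if the ratio of conditional power to initial power falls below the proportion of remaining information time". Its example is an initial power of 85% with 40% of information remaining, which requires conditional power above 34%. No information times are given for this assessment. Appendix G says that the DSMB "will be assembled twice per year".
- **Efficacy.** Up to three looks at about 40%, 60% and 80% information use a critical value of 3.291, and the final test uses 1.965. The section describes the power cost of this adjustment as negligible.

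Appendix C supplies the constants: "Our expected power of 85.8% implies that our expected z-score at the end of the trial is 3.031". From these it derives a final standard error of 0.2287 and a final information of 19.1. Nowhere does the plan give the power cost of the futility guideline.

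**The concern.** A futility rule stops some trials that would have gone on to succeed. Leaving it non-binding protects the type I error rate but not the power: whenever the guideline is followed, power falls. The 4.0% row of Table 5 clears 80% by only 1.6 points, so a small loss is enough to cancel the sentence that supports keeping 5270 subjects.

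The guideline also asks most of the data when there is least of it. The required conditional power is initial power times the remaining information, so the earliest look has the highest bar. Because futility is tied to DSMB meetings with no minimum information fraction, the cost depends on a schedule that the plan leaves open.

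**Working it through.** **Step 1: reproduce Table 5.** At 5270 subjects, Table 4 and the assumed 20% Korean share of further enrolment give 1275 + 0.20 × (5270 − 4467) = 1435.6 Korean and 3834.4 North American subjects. Carriers number 0.59 × 1435.6 + 0.28 × 3834.4 = 1920.6, or 1824.6 after 5% dropout. Reading the event rate as the average over both arms gives 82.1 events at 4.5% and 73.0 at 4.0%. The Freedman formula is power = Φ(√E × (1 − HR)/(1 + HR) − 1.960).

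- 4.5%: Φ(√82.1/3 − 1.960) = 85.6% (plan 85.8%)
- 4.0%: Φ(√73.0/3 − 1.960) = 81.3% (plan 81.6%)

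A two-proportion calculation on the same inputs gives 85.8% and 81.5%. So the Table 5 figures are recovered with no interim stopping.

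**Step 2: the futility boundary.** The expected final z-score is θ = 1.960 + z(P0), which is 3.031 for P0 = 85.8% (as in Appendix C) and 2.860 for P0 = 81.6%. With t the information time and benefit counted as positive,

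CP = 1 − Φ[(1.960 − Z√t)/√(1 − t) − θ√(1 − t)].

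This is the Appendix C formula with the drift term read inside Φ. As printed, the term stands outside and gives impossible values (−2.17 at t = 0.4, Z = 1.96). That may be an extraction artefact. Setting CP = P0(1 − t) and solving for Z:

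| Information time | CP required, P0 85.8% | Z boundary | CP required, P0 81.6% | Z boundary |
|---|---|---|---|---|
| 40% | 51.5% | 0.27 | 49.0% | 0.35 |
| 60% | 34.3% | 0.64 | 32.6% | 0.69 |
| 80% | 17.2% | 1.04 | 16.3% | 1.06 |

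**Step 3: power with the guideline followed.** The z-process is treated as Brownian motion with drift θ, efficacy bound 3.291 at 40/60/80%, final value 1.965, and a stop whenever Z is below the futility boundary. A numerical recursion and simulations of 1 to 2 million paths agree.

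| True HR 0.50 | 4.5% rate | 4.0% rate |
|---|---|---|
| Table 5 | 85.8% | 81.6% |
| Efficacy boundary only | 85.7% | 81.5% |
| Futility followed at 40/60/80%, P0 and information rescaled to the scenario | 83.2% | 78.1% |
| Chance of a futility stop, same setting | 8.7% | 12.2% |

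**Step 4: the 4.0% case with the Appendix C constants.** Final information at 4.0% is (2.860/ln 2)² = 17.0, which is 0.89 of 19.1. Looks at 40/60/80% of 19.1 therefore fall at 45%, 67% and 90% of what that trial would accrue.

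- P0 kept at 85.8%, information time rescaled to the 4.0% trial: 78.7%
- P0 kept at 85.8%, information time measured against 19.1: 79.9%

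**Step 5: dependence on timing.** A single futility look at 4.0% (P0 81.6%) gives 78.9% at t = 0.4, 79.7% at 0.5, 80.3% at 0.6 and 81.0% at 0.8. As an assumed schedule, not one in the plan, adding one futility look at 20% to the three gives 79.6% at a 4.5% rate and 73.6% at 4.0%. With the constants held at 85.8% and 19.1, the same calculation gives 76.7% at 4.0%.

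**The case against.** The guideline is advisory. The DSMB would also see unconditional power at current event rates and a confidence interval for the event rate, and Appendix G lets it advise a larger sample if events run low, which is the 4.0% scenario. Treating the guideline as an automatic stop therefore gives an upper bound on the loss at those looks. This stands, and the conclusion is limited to the case in which the guideline is followed.

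The 4.0% row is a sensitivity row. The base case is 4.5%, and section 15.2.2 reports an observed rate of 4.8% in carriers. At 4.5% power stays above 80% at the three looks. This also stands.

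Under the plan's own constants the 4.0% figure is 79.9%, which is 80% to rounding. This is a fair reading and is why a range is given. It does not restore the 81.6% in the table, nor does it leave any margin under the 80% sentence.

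Three stronger conclusions might be inferred, and the documents do not support them:

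- **Table 5 is miscalculated.** It is not; it reproduces as fixed-sample power.
- **Semi-annual DSMB meetings imply six or eight futility looks and a large loss.** The plan sets no such series and no look at 20%. The information fraction at each meeting cannot be derived from the documents.
- **Conditional power follows the current trend, which would give 63.7% at 4.0%.** The Appendix C formula carries the design power P0, so the design effect is the better-supported reading.

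**Conclusion.** The stated powers and the 80% sentence hold only if no trial is stopped for futility. With the guideline followed at 40/60/80% information, the loss is about 2.6 points at a 4.5% rate (85.8% to 83.2%) and about 1.7 to 3.5 points at 4.0% (81.6% to between 79.9% and 78.1%). The 4.0% claim is thus lost or left with nothing to spare, while the base case remains adequately powered. To keep 80% at 4.0% on the rescaled reading would need a fixed-sample power of about 83.2%, or some 4% more information.

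The result assumes a true hazard ratio of 0.50, conditional power at the design effect with the drift term inside Φ, full adherence to an advisory guideline, and futility looks that coincide with the efficacy looks. The last is an assumption, because section 15.8 names only DSMB reviews.

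**What to change.** 1. Add a column to Table 5 with power when the futility guideline is followed at 40/60/80% information: about 83% at a 4.5% rate and 78% to 80% at 4.0%. State which P0 and which final information are used.
2. Qualify the sentence that 5270 subjects give at least 80% power at event rates of 4.0% or more, so that it applies without futility stopping.
3. State in section 15.8 that the futility guideline is assessed at the same 40%, 60% and 80% looks as efficacy. This limits further loss from earlier or more frequent looks but does not by itself bring the 4.0% case back to 80% on the rescaled reading.

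The cost is a slightly less favourable stated power, a few sentences, and no formal futility look before 40% information. No change in sample size or data collection is required.
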